evaluate the safety and tolerability of the planned regimens, and to determine the recommended dose for the monotherapy and combination therapy arms for the randomized phase.

The safety run-in will utilize a 3+3 design to include at least 3 subjects treated with monotherapy at the dose and schedule expected to be used in combination, as well as at least 3 subjects treated with combination therapy to evaluate safety and tolerability. The monotherapy arm will be enrolled first to confirm the expected safety profile of CC-486 alone at the planned dose and schedule in the target population.

Data from the safety run-in will be reviewed in conjunction with the study investigators, Scientific Steering Committee, and Data Monitoring Committee to ensure agreement with the recommended Phase 2 dosing regimens prior to beginning enrollment to the randomized treatment phase.

The randomized treatment phase will be conducted in 2 stages, with a futility assessment planned at the completion of Stage 1 to determine whether the null hypothesis ($H_0: p < 12.5\%$) can be rejected with 3 or more responses in Stage 1. If 3 or more responses have been observed before the end of Stage 1, the planned futility assessment may be performed earlier than at the completion of Stage 1 to confirm the finding of responses. This earlier analysis will replace the futility analysis planned at the completion of Stage 1. This earlier futility assessment will have the same integrity as the futility assessment planned at the completion of Stage 1. An analysis will be performed at the completion of Stage 2 to estimate the **overall** response rate of treatment of all the subjects in the cohort. All subjects who receive investigational product (IP) in this study will continue to be followed for information related to post-treatment safety and subsequent MDS therapies, as described in Section 4.1.5.

Approximately 10-12 evaluable subjects randomized to the combination treatment arm at selected study centers will participate in PK sampling procedures as described in Section 6.10.

Extension Phase

At the Investigator's discretion and following confirmation of eligibility criteria below, subjects can enter the Extension Phase (EP):

Eligibility Criteria:

- Subjects who have signed the informed consent for the EP of the study;

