Subjects will undergo screening procedures over a period of up to 28 days following the signing of their informed consent document (ICD). Eligible subjects will continue to the safety run-in or the randomized treatment phase of the study where they will receive IP for up to six 28-day treatment cycles. Those who derive benefit from the treatment may continue IP until loss of that benefit (Section 4.1.3).

After treatment discontinuation, subjects will be followed for 28 days for CC-486 safety-related issues and 90 days for durvalumab safety-related issues. After that, subjects will be contacted by telephone every 3 months in the follow-up phase of the study.

The enrollment period for this study is expected to last approximately 39 months. The treatment and follow-up periods are expected to conclude approximately 12 months after the last subject is enrolled. The Extension Phase is expected to last approximately 24 months. Therefore, the total duration of the study is expected to be approximately 75 months.

The *End of Trial* is defined as either the date of the last visit of the last subject to complete the study, or the date of receipt of the last data point from the last subject that is required for primary, secondary and/or exploratory analysis, as pre-specified in the protocol and/or the Statistical Analysis Plan (SAP), whichever is the later date.

The study will conclude once all subjects have completed or discontinued from the Extension Phase.

Study Treatment (Investigational Product – IP)

CC-486 (Oral Azacitidine)

Eligible subjects who are assigned to the monotherapy treatment arm will receive CC-486 at the dose and schedule identified during the safety run-in phase of the study. Dose and schedule may be reduced to manage toxicity or increased as described in Section 8.2. Subjects can continue treatment with CC-486 as long as all protocol-specified re-treatment criteria continue to be met (see Section 8.2.5).

Durvalumab (MEDI4736)

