4.1.2. Safety Run-in

The safety run-in will utilize a conventional 3+3 design to find a tolerable dose for the randomized treatment phase. The subjects will be treated with CC-486 first to confirm the expected safety profile of CC-486 alone at the planned dose and schedule in the target population. The maximum administered dose (MAD) of CC-486 will not exceed 300 mg BID (21/28 days). The resulting tolerable dose of CC-486 will then be used to combine with durvalumab 1500 mg for the combination therapy.

The completion of the CC-486 safety run-in has determined 100 mg BID, 21/28 day regimen (dose level -2) as the CC-486 dose to proceed into the combination therapy safety run-in.

The dose-finding procedure for CC-486 and CC-486+durvalumab will proceed as following.

Part (A) - starting dose for CC-486 as monotherapy: A group of 3 subjects will receive CC-486 at dose level 0 (200 mg BID (21/28 days) and will be closely monitored through at least 2 treatment cycles for dose-limiting toxicities, as defined in Section 4.1.2.1. If for any reason the monotherapy safety run-in starting dose needs to be reduced, the starting dose will follow the established levels in [Table 1](#).

1. If #Subject with DLT = 0/3, the dose will be declared tolerable and used as the starting CC-486 dose.
2. If #Subject with DLT = 1/3, recruit another 3 subjects to test the same dose.
 - a. If #Subject with DLT = 1/6, the dose will be declared tolerable and used as the starting CC-486 dose.
 - b. If #Subject with DLT \geq 2/6, the dose will be declared intolerable and the next lower dose level of CC-486 according to [Table 1](#) will then be explored. Repeat the entire procedure with 3 new subjects.
3. If #Subject with DLT \geq 2/3, the dose will be declared intolerable and the next lower dose level of CC-486 according to [Table 1](#) will then be explored. Repeat the entire procedure with 3 new subjects.

The safety run-in for CC-486 monotherapy has been completed as of December 2016.

Part (B) - starting dose for CC-486+durvalumab as combination therapy: A group of 3 subjects will receive CC-486 dose determined in Part (A) above plus durvalumab 1500 mg (given by IV infusion [over 1 hour \pm 5 minutes] on Day 1 of each 28-day treatment cycle) and will be closely monitored through at least 2 treatment cycles for dose-limiting toxicities, as defined in Section 4.1.2.1.

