6.5. CC-486 (Oral Azacitidine)

All eligible subjects will receive treatment with CC-486 at the dose and schedule identified during the safety run-in. Dose and schedule may be decreased as described in Section 8.2.4 in order to manage toxicity. In the absence of unacceptable toxicity, subjects who show signs of worsening

disease (clinical or hematological), who remain in stable disease, or do not experience modified IWG 2006 hematologic improvement (HI) or better (PR, CR or marrow CR – modified IWG 2006, [Appendix F](#)) after 2 well-tolerated cycles, may have their **dose increased** at the discretion of the investigator and in discussion with the medical monitor as defined in [Table 3](#). Again, dose and schedule may be adjusted as described in [Section 8.2.4](#) in order to manage toxicity.

After at least 2 treatment cycles at the increased dose, the assigned dose can be further increased if it is well-tolerated but no objective response is observed.

Special attention should always be given to potential drug-related toxicity and/or tolerability issues so dose and/or schedule can be reduced appropriately ([Section 8.2.4](#)).

Subjects can continue treatment with CC-486 as long as all protocol-specified re-treatment criteria continue to be met (see [Section 8.2.5](#)).

Best supportive care should be used in combination with study treatment as deemed necessary. Best supportive care includes, but is not limited to, treatment with RBC transfusions (pRBC or whole blood), single donor or pooled donor platelet transfusions, antibiotic, antiviral and/or antifungal therapy, antiemetic and/or antidiarrheal support, nutritional support as needed, and granulocyte (or granulocyte macrophage) colony-stimulating factors for subjects experiencing neutropenic fever or infection, and may be given as secondary prophylaxis ([Section 9.1](#)). Best supportive care for this study excludes the use of ESAs and other hematopoietic growth factors, except as noted for G- or GM-CSF in [Section 9.1](#). It is recommended that an antiemetic medication such as ondansetron or an appropriate locally-available equivalent be taken 30 minutes prior to CC-486 administration during Cycle 1 of the treatment phase. If nausea/vomiting is not significant, further antiemetic prophylaxis may not be needed.

Refer to [Section 8.2](#) for details regarding IP dispensation, administration, and accountability.

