8.2. Treatment Administration and Schedule

After the safety run-in is complete and the CC-486 dose and regimen to be used in combination with durvalumab is established, eligible subjects will be randomized to receive CC-486 alone or in combination with durvalumab in the randomized treatment phase of the study. All randomized subjects will receive CC-486 orally administered tablets at the established dose and schedule. The schedule will include BID dosing on days 1-21 of each 28-day treatment cycle. Subjects randomized to the combination therapy arm will receive durvalumab, 1500 mg on Day 1 of each 28-day treatment cycle by IV infusion over approximately 1 hour (\pm 5 minutes). CC-486 tablets should be ingested approximately 1 hour after completion of the durvalumab infusion on Day 1 of each treatment cycle (except for Cycle 1 in which CC-486 is given on Day -1 for PK sub-study subjects) as described in Section 8.2.2. In the event of unacceptable toxicity, CC-486 dose and schedule may be modified (see Section 8.2.4). Infusions of durvalumab may be interrupted, slowed, or discontinued in order to address toxicity, but dose reduction of durvalumab is not permitted (see Section 8.2.4.2).

In the absence of unacceptable toxicity, subjects who show signs of worsening disease (clinical or hematological), who remain in stable disease, or do not experience modified IWG 2006 hematologic improvement (HI) or better (PR, CR or marrow CR – modified IWG 2006, [Appendix F](#)) after 2 well-tolerated cycles, may have their **dose increased** at the discretion of the investigator and in discussion with the medical monitor as described in Section 8.2.4 and [Table 3](#). Again, dose and schedule may be adjusted as described in Section 8.2.4 in order to manage toxicity.

Subjects may continue to receive the protocol-prescribed therapy for as long as they benefit from the treatment (Section 4.1.3) or until treatment is discontinued for reasons detailed in Section 12.

Prior to discontinuing a subject, it is recommended that the investigator contact the medical monitor and forward appropriate supporting documents for review and discussion. However, the decision to discontinue a subject remains the responsibility of the treating physician and will not be delayed or refused by the sponsor.

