In the absence of unacceptable toxicity, subjects who show signs of worsening disease (clinical or hematological), who remain in stable disease, or do not experience modified IWG 2006 hematologic improvement (HI) or better (PR, CR or marrow CR – modified IWG 2006, [Appendix F](#)) after 2 well-tolerated cycles, may have their **dose increased** at the discretion of the investigator and in discussion with the medical monitor as described in [Section 6.5](#) and [Table 3](#). Again, dose and schedule may be adjusted as described in [Section 8.2.4](#) in order to manage toxicity.

After Amendment 4 approval, dose increases will no longer be allowed. Dose decreases following Table 3 are still allowed. Subjects will continue at the same dose levels during the Extension Phase. Any potential dose escalation will be considered a treatment failure and the subject should be discontinued.

Refer to Section 8.2.5 if, despite temporary interruption, delay or modification of study treatment, the toxicity persists for more than 42 days and is considered by the investigator to be at least possibly related to study treatment.

Following any modification of study treatment or if a dose is missed, the subject should stay on the visit schedule as specified in Table 2. Unscheduled visits may occur to monitor the subject's toxicities if necessary.

Table 3: CC-486 Dose Modification Steps

Dose Modification Step	BID Dose and Schedule Days	Rescue Step	Rescue (QD) Dose and Schedule (Days)
+2	300 mg BID, 21/28		
+1	250 mg BID, 21/28		
0 ^a	200 mg BID, 21/28		
-1	150 mg BID, 21/28	R+2	300 mg QD, 21/28
-2	100 mg BID, 21/28	R+1	200 mg QD, 21/28
-3 ^b	100 mg BID, 14/28	Rescue (R)	200 mg QD, 14/28

BID = twice daily; QD = once daily; R = rescue dose step.

^a Highest starting dose to be evaluated.

^b Any subject who cannot tolerate dose modification Step -3 (or R) will discontinue IP and enter the follow-up period.

→ Dose adjustment options from current dose/regimen. Dose/schedule reduction does not need to be taken stepwise.

Dose Modification for Febrile Neutropenia

Any subject who experiences febrile neutropenia \geq Grade 3 that persists for up to 3 days may, with concomitant antibiotic, antiviral, and/or antifungal therapy, continue to receive IP uninterrupted at the investigator's discretion. If the event exceeds 3 days, IP should be temporarily interrupted. Dose modification may be considered as summarized in Table 4.

Dose Modification for Neutropenia Grade 4

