For subjects entering the study with pre-existing Neutropenia Grade 4, treatment should be started at the regular starting dose and schedule of 200 mg BID 21/28d. However, if neutropenia continues to worsen under treatment, dose modification may be considered as summarized in Table 4.

For any subject who experiences a worsening of neutropenia to Grade 4 for ≥ 4 days, independent of whether considered related to IP or not, a dose modification may be considered as summarized in [Table 4](#).

Dose Modification for Diarrhea

It is recommended that subjects experiencing diarrhea be managed according to the guidelines provided in [Appendix H](#). Anti-diarrhea medication may be administered as prophylaxis against diarrhea and for treatment of any adverse events of diarrhea. Recommended dose modification steps for diarrhea (\geq Grade 2) are summarized in [Table 4](#). If further dose-reduction beyond modification Step -3 (or the QD *rescue* regimen) is thought to be necessary, IP should be discontinued and the treatment discontinuation visit scheduled.

Dose Modification for Nausea and Vomiting

A serotonin (5-HT₃) receptor antagonist (eg, ondansetron) or other comparable medication may be administered as an antiemetic prophylaxis approximately 30 minutes prior to IP administration if necessary. Antiemetic pretreatment is recommended during the first cycle of the treatment phase. If the subject does not experience significant nausea and/or vomiting, further use of antiemetic medications may not be necessary. Antiemetic medication(s) should be administered for treatment of any adverse events of nausea and/or vomiting. Recommended dose modifications for nausea and vomiting (\geq Grade 3) are summarized in [Table 4](#). If further dose-reduction beyond modification Step -3 (or the QD *rescue* regimen) is thought to be necessary, IP should be discontinued and the treatment discontinuation visit scheduled.

Dose Modification for Renal Dysfunction and Abnormal Serum Electrolytes

If unexplained elevations of serum creatinine or electrolyte disturbances occur, dose or schedule modifications may be implemented as summarized in [Table 4](#). If further dose-reduction beyond modification Step -3 (or the QD *rescue* regimen) is thought to be necessary, IP should be discontinued and the treatment discontinuation visit scheduled.

Dose Modification for Weight Change

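### Section 8.2.4.1 starts subjects with pre-existing Grade 4 neutropenia on CC-486 200 mg BID, twice the 100 mg BID that the completed run-in set and that other sections apply without exception

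*Protocol*

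**What the plan says.** Under the Grade 4 neutropenia heading, Protocol Section 8.2.4.1 says of subjects who already have that grade at entry that "treatment should be started at the regular starting dose and schedule of 200 mg BID 21/28d". It then allows modification under Table 4 if the count worsens on treatment.

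The rest of the protocol takes the starting dose from the safety run-in:

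- Protocol Summary, Study Design: one purpose of the run-in is "to determine the recommended dose for the monotherapy and combination therapy arms for the randomized phase".
- Section 4.1.2: "The completion of the CC-486 safety run-in has determined 100 mg BID, 21/28 day regimen (dose level -2", and that dose is carried into the combination run-in.
- Protocol Summary, Study Treatment: subjects "assigned to the monotherapy treatment arm will receive CC-486 at the dose and schedule identified during the safety run-in phase". The combination arm receives CC-486 on the same terms.
- Section 6.5: "All eligible subjects will receive treatment with CC-486 at the dose and schedule identified during the safety run-in".
- Section 8.2: "All randomized subjects will receive CC-486 orally administered tablets at the established dose and schedule".
- Table 3, footnote a, on step 0 (200 mg BID, 21/28): "Highest starting dose to be evaluated".

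None of these makes an exception for baseline neutropenia. The Table 4 row for pre-existing Grade 4 neutropenia gives no starting dose.

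**The concern.** The sentence in 8.2.4.1 does not set a special dose for neutropenic subjects. It says they should have the regular dose, with no reduction in advance, and then states the wrong figure. A site that followed it literally would double the starting dose in the subjects with the lowest neutrophil counts. Such subjects can enter: Section 7.3 sets no minimum neutrophil count, and both 8.2.4.1 and Table 4 provide for them.

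With enrollment closed, what remains is how the collected data are read. If a randomized-phase subject did start at 200 mg BID, the protocol gives two answers on whether that start was correct, and so on whether it was a deviation. SAP Section 6 tabulates deviations, and SAP Section 5.2.4 removes subjects with major deviations from the evaluable population used for supportive efficacy analyses. The documents do not say whether such a start would count as major.

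**Working it through.** **Inputs**

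- Starting dose in 8.2.4.1: 200 mg BID, 21 of 28 days (Table 3 step 0).
- Run-in result in 4.1.2: 100 mg BID, 21 of 28 days (dose level -2; Table 3 step -2).
- The plan gives no per-day or per-cycle totals, so there is no stated total to reproduce.

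**Dose arithmetic**

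Daily dose = dose × 2. Cycle dose = daily dose × 21.

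| | Daily dose | Dose per cycle (21 dosing days) |
|---|---|---|
| 8.2.4.1 | 200 × 2 = 400 mg | 400 × 21 = 8,400 mg |
| Run-in dose | 100 × 2 = 200 mg | 200 × 21 = 4,200 mg |
| Ratio | 2.0 | 8,400 / 4,200 = 2.0 |

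The two doses are two levels apart (0 versus -2).

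**Does the run-in dose govern the randomized phase?** The sentence in 4.1.2 reporting the result names only the combination run-in. The link to the randomized phase comes from other text. The Summary says the run-in sets the dose for both randomized arms, 4.1.2 opens by saying the run-in looks for a tolerable dose for that phase, and the Summary, 6.5 and 8.2 apply its result. Section 4.2 describes 200 mg BID only as the first dose to be tested. No current text reconciles 8.2.4.1 with these sections.

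**When could a subject starting at 100 mg BID reach 200 mg BID?** Section 6.5 allows an increase after 2 well-tolerated cycles, so Cycle 3 at the earliest. It adds: "After at least 2 treatment cycles at the increased dose, the assigned dose can be further increased".

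- One Table 3 step at a time: 100 mg BID in Cycles 1-2, 150 mg BID in Cycles 3-4, 200 mg BID from Cycle 5.
- If the first increase may skip a step: 200 mg BID from Cycle 3.

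The documents do not say which applies. The stepwise wording in 8.2.4.1 concerns a return to the original dose after a reduction. The earliest point is therefore Cycle 3 to Cycle 5, against Cycle 1 under 8.2.4.1. Any increase also requires worsening or lack of response, and discussion with the medical monitor.

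**Context only.** The amendment summary that reports the run-in outcome says the starting dose was lowered to 100 mg BID for the combination run-in and Phase 2 monotherapy. It lists 4.1.2, Table 1 and Table 3 as revised, and not the neutropenia paragraph. That fits a missed update, but the conflict stands on the current text alone.

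**The case against.** The best case on the other side is that the sentence can no longer do harm. It governs only starting doses. The last subject enrolled in June 2018, and after Amendment 4 no dose may be increased. SAP Section 8 builds its exposure measures (cumulative dose, average daily dose, dose intensity) from doses taken, and a by-subject exposure listing is already planned. The 200 mg figure also once had a proper referent, since run-in subjects at dose level 0 were to start there.

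Most of this stands, and it limits the consequence. It does not rescue the figure. The sentence is not confined to the run-in, and it calls 200 mg BID the regular dose in a protocol that reports the monotherapy run-in as complete at 100 mg BID.

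A reader might infer more than the documents support:

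- *That a 200 mg BID start complies with 8.2.4.1 and is also a reportable overdose.* Section 8.2.6 defines overdose against the dose assigned to the individual subject. Someone assigned 200 mg BID who takes it is not overdosed on that definition. The open question is whether the right dose was assigned, which is a deviation question.
- *That 200 mg BID failed because of neutropenia.* No dose-limiting toxicity counts are given, and the only run-in problem named, in an amendment summary, is gastrointestinal intolerability.
- *That subjects were in fact double-dosed.* Nothing shows that any randomized-phase subject started at 200 mg BID.

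**Conclusion.** The point holds as an internal inconsistency. Section 8.2.4.1 states a starting dose 2.0 times the one that the Protocol Summary, 6.5 and 8.2 require. This rests on reading the dose those sections refer to as the 100 mg BID result in 4.1.2, which is the only run-in result the protocol reports. That the figure was simply not updated is an inference, though a likely one.

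It should be corrected because it is a wrong number in a dosing instruction and the correction is nearly free. The practical effect is small. The number of subjects affected is not given and may be zero, no future subject will start under this text, and the Stage 1 stop, which depends on response counts already observed, is unaffected.

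**What to change.** 1. In the Grade 4 neutropenia paragraph of Section 8.2.4.1, replace the 200 mg BID 21/28d figure so that the regular starting dose and schedule is the one *identified in the safety run-in (100 mg BID, 21/28 days)*.
2. Cross-check the by-subject exposure listing (SAP Section 8) against baseline neutrophil count (baseline as defined in SAP Section 11.2). Look for any randomized-phase subject with baseline Grade 4 neutropenia who started at 200 mg BID. Keep the check to the randomized phase, because a 200 mg BID start was planned for run-in subjects at dose level 0. Report any such case with the safety and response results and state whether it was treated as a deviation. If there are none, say so.

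The cost is one phrase and one check of data the SAP already plans to list. No new procedure or analysis is needed.
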